5.8 Outcomes Research Assessments

Not applicable.

5.9 Other Assessments

5.9.1 Height and Body Mass Index (BMI)

- Measurement of height should be performed with the subject's shoes removed. The subject's knees should be straightened, head held erect and eyes forward
- Weight must be recorded using a calibrated scale, preferably the same scale at each clinic visit. Subject should remove shoes and heavy clothing before standing on scale.
- BMI is used as an index of obesity and is a method of defining normal body weight and excess body fat. It correlates in a population with percent body fat. BMI is determined by weight, (kg) divided by height (m) squared

Method of BMI Calculation:

- Use actual height and weight
- To calculate BMI:
 - Convert pounds (lbs) to kilograms ($\text{kg} = \text{lb} / 2.2$)
 - Convert inches (in) to centimeters ($\text{cm} = \text{in} \times 2.54$)
 - $\text{BMI} = (\text{weight in kg}) / (\text{height in cm}/100)^2$
 - Round to one decimal place (if 0.05 or greater, round up)

The BMI calculation is used for assessment for inclusion. All analysis calculations for BMI will be derived internally by BMS using the weight and height at the specified time point or the most recent high measurement (if not applicable).

5.9.3 Other Supplemental (Unscheduled Visits)

At any time during the study, the Investigator may at his/her discretion, arrange for a subject to have an unscheduled (supplemental) assessment(s) including immunogenicity especially in the case of AEs that require follow-up. If the subject is seen for an unscheduled assessment, the appropriate Supplemental Pages of the eCRF must be completed.

5.10 Results of Central Assessments

Centrally analyzed DXA and MRI data supporting eligibility will be returned to the site. Any subsequent imaging results from centralized analyses will not be returned to the site. Safety samples will be assayed at a Central Laboratory and results returned to the Site.

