5.3 Safety Assessments

5.3.1 Safety Imaging Assessment for the Study

Image acquisition guidelines and submission processes will be outlined in the MB130045 Imaging Manual, to be provided by the central imaging lab.

A central imaging lab will perform all imaging analyses.

The clinical site will be trained in imaging procedures prior to scanning the first study subject. Images will be submitted to the central imaging lab for central review. The site will be informed of quality issues or needs for repeat scanning via queries from the central imaging lab.

Any incidental findings of potential clinical relevance that are not directly associated with the objectives of the protocol should be evaluated and handled by the Study Investigator as per standard medical/clinical judgment.

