5.3.1.1 DXA

DXA is recognized as the reference method to measure BMD as well as soft-tissue composition (body composition: lean mass, fat mass) with acceptable accuracy errors and good precision and reproducibility. Subjects with a centrally read screening DXA T-score (total spine, total hip or femoral neck) greater than a -2.5 S.D. will be enrolled and randomized for treatment. Adequacy of DXA scans should also be confirmed by the central imaging lab prior to randomization.

Screening results to confirm eligibility (DXA T-score) will be returned to the site by the central imaging lab. No other results will be provided to the site.

Bone imaging (hip and lumbar spine) will be performed at all imaging facilities and body composition (whole body), an exploratory measure, will be additionally carried out at imaging facilities with the appropriate hardware/software.

DXA will be conducted at baseline, end of treatment (Day 112, +/- 1 week) and approximately 6 months after the end of the treatment (Day 292, +/- 2 weeks).

Screening DXA should be performed approximately 21 days prior to the Day 1 dose. Eligibility should be confirmed by central imaging lab prior to entry into the lead-in period (Day -7).

A repeat DXA may be performed if clinically indicated.

Imaging assessments will be performed at time points indicated in [Table 5.1-1](#), [Table 5.1-2](#) and [Table 5.1-3](#).

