6.7 Other Safety Considerations

Any significant worsening noted during interim or final physical examinations, electrocardiogram, x-ray filming, any other potential safety assessment required or not required by protocol should also be recorded as a nonserious or serious AE, as appropriate, and reported accordingly.

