8.3 Endpoints

8.3.1 Primary Endpoint(s)

The primary objective to assess the effect of daily or weekly doses of BMS-986036 on safety, tolerability and hepatic fat fraction (%) by MRI in patients with biopsy proven NASH will be assessed by the primary endpoint of:

- Change in percent hepatic fat fraction (%) by MRI from baseline to Week 16.
- Safety endpoints include incidence of AEs, serious AEs, and events of special interest including injection site assessment, AEs leading to discontinuation, and death as well as marked abnormalities in clinical laboratory tests, vital sign measurements, ECGs, physical examinations and bone mineral density (BMD) collected by DXA scan at specified time points in [Table 5.1-1](#), [Table 5.1-2](#) and [Table 5.1-3](#).

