4.2 Safety Endpoints

The primary safety endpoints include incidence of AEs, serious AEs, and events of special interest including injection site assessment, AEs leading to discontinuation, and death as well as marked abnormalities in clinical laboratory tests, vital sign measurements, ECGs, physical examinations and bone mineral density (BMD) collected by DXA scan at specified time points in Table 5.1-1, Table 5.1-2 and Table 5.1-3 of the Protocol.

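### A fall in bone mineral density seen only on the scheduled Day 112 or early-termination DXA has no visible route to the investigator or the AE record, although BMD is a primary safety endpoint

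*Protocol*

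**What the plan says.** **Status of BMD.** Under Primary Endpoint(s), protocol 8.3.1 names among the safety endpoints "bone mineral density (BMD) collected by DXA scan at specified time points". SAP 4.2 begins "The primary safety endpoints include incidence of AEs, serious AEs, and events of special interest", and its list goes on to "physical examinations and bone mineral density (BMD) collected by DXA scan at specified time points in" the protocol's schedule tables.

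**AE recording.** Protocol 6.7 starts from "Any significant worsening noted during interim or final physical examinations" and extends to "any other potential safety assessment required or not required by protocol should also be recorded as a nonserious or serious AE", as appropriate.

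**Who reads the scans and who sees the results.** Protocol 5.3.1 states: "A central imaging lab will perform all imaging analyses". Under 5.3.1.1 the screening T-score is returned to confirm eligibility, and then: "No other results will be provided to the site". Section 5.10 applies the same rule to all later imaging: "Any subsequent imaging results from centralized analyses will not be returned to the site". Section 5.10 also says that central results from safety samples do go back to the site.

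**Reporting of BMD.** Protocol 8.4.3 and SAP 7.6 both say that BMD results will be tabulated.

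**The concern.** Protocol 1.5 names bone effects as one of three potential risks to be explored, with immunogenicity and injection site reactions. Section 1.5.1 gives the purpose of the DXA scans as finding any acute or sustained effect on BMD. The scans sit under Safety Assessments.

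Withholding on-study results makes sense for hepatic fat fraction, the primary efficacy measure, because returning it could weaken the blind. The visible text gives no reason for extending the rule to bone. The restrictive sentence in the DXA section is the same as the one in the MRI section (5.4.1.1), which suggests it was carried across.

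Section 6.7 depends on someone at the site noticing a worsening. If the site never sees the on-study BMD, a loss that shows only on the scan goes unrecorded as an AE, no physician judges its relation to study drug, and neither the subject nor the investigator learns of it. It also cannot count towards the ad hoc DMC meetings in protocol section 7, because both of those triggers count graded AEs.

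**Working it through.** The plan states no figure to reproduce here. The check sets the sections side by side and compares the scan dates with the AE window.

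**Step 1. Does 6.7 reach BMD?** Yes. DXA is a safety assessment (5.3.1.1) and BMD is a safety endpoint (8.3.1, SAP 4.2). Section 6.7 covers any other safety assessment, whether or not the protocol requires it.

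**Step 2. Can the site note a change?** All DXA analysis is central (5.3.1). Only the screening T-score is returned (5.3.1.1), and later central results are not (5.10). The scheduled post-baseline scan therefore gives the investigator nothing to note.

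**Step 3. Does timing allow an AE?** Inputs:
- treatment runs to Day 112 (3.1)
- end-of-treatment DXA at Day 112 ± 7 days, follow-up DXA at Day 292 ± 14 days (5.3.1.1)
- non-serious AEs collected until 30 days after dosing stops (Table 5.1-1)

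| Item | Arithmetic | Result |
|---|---|---|
| AE window closes | 112 + 30 | about Day 142 |
| Latest end-of-treatment DXA | 112 + 7 | Day 119, inside |
| Day 292 DXA, days after last dose | 292 − 112 | 180, outside |
| Earliest Day 292 DXA, days after last dose | 292 − 14 − 112 | 166, outside |

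For the Day 112 scan, non-return of the result is the only obstacle. The same holds for an early-termination scan done within 30 days of the last dose. The Day 292 scan has a second barrier: a non-serious change would fall outside AE collection even if the result were returned.

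**Step 4. Is there another route in the visible text?**
- *Incidental findings (5.3.1):* limited to findings not tied to the protocol's objectives. BMD belongs to the primary safety objective, so this does not clearly apply.
- *Repeat DXA (5.3.1.1):* allowed if clinically indicated, but nothing says who receives the result.
- *DMC (section 7):* AEs, laboratory values and available efficacy data are named. BMD is not, although the list is open-ended.
- *SAP limits:* ECG and vital signs have numerical criteria and laboratory tests have toxicity grades (SAP 7.6.4 to 7.6.6). The visible text gives no limit for a significant BMD change.

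No visible passage carries an on-study BMD result to the investigator, the Medical Monitor or the DMC.

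**The case against.** The strongest reply is that nothing is breached and little is lost.

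- **The wording of 6.7.** It speaks of *significant* worsening that is *noted*, and says *should*. A reader might infer that the plan sets a firm duty and then forbids it. The text does not support that: a result nobody at the site sees has not been noted. This is a gap between a general AE rule and a specific imaging rule.
- **Other ways into the AE record.** A reader might infer that bone harm can never appear there. That goes too far. A fracture is an ordinary AE, and unscheduled assessments (5.9.3) and a clinically indicated repeat DXA are allowed. The gap covers changes seen only on the scheduled central scan.
- **Group inference.** A reader might infer that a trial with no bone AEs would be uninformative about bone. AE tables are not the planned measure of BMD, which is tabulated in its own right. That comparison is intact.
- **The DMC.** It may ask for unblinded data by group or by subject, and its procedures are in a separate charter. An alert route there, in the imaging manual or in redacted text cannot be excluded.
- **Low stakes.** Section 1.5.1 rates the bone risk as low, and entry criteria exclude low T-scores and recent fracture. The scheduled scan comes at the end of treatment, so its result would rarely bear on dosing.

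All of this stands, and it limits the point to individual-level capture and awareness. It does not supply the missing route for the Day 112 and early-termination scans. The different handling of safety laboratory results in the same section (5.10) remains unexplained.

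**Conclusion.** The point holds in this limited form and is a cheap improvement. A BMD fall found only on the Day 112 or early-termination scan has no visible path to the investigator or the AE record, although that scan measures a primary safety endpoint and falls inside the AE window. What is affected is individual AE capture, assessment of relatedness, awareness at the site, and the AE-based DMC triggers. The group BMD results are not affected.

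The documents do not allow an estimate of how many subjects would have a significant fall. They give no DXA precision, no grading of BMD change and no expected loss. The T-score limit of −2.5 is an entry criterion only and should not be read as a threshold for on-study worsening.

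The conclusion assumes that the last dose is at about Day 112, that an early-termination scan is done within 30 days of the last dose, and that the charter, imaging manual and redacted text contain no alert route. If one of them does, the remedy reduces to a cross-reference in the protocol.

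**What to change.** Reconcile 5.3.1.1 and 5.10 with 6.7:

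1. Confine the blanket no-results rule to the efficacy and exploratory imaging (MRI, MRE and whole-body composition).
2. Have the central imaging lab report post-baseline hip and spine BMD that meets a limit set in advance by the sponsor, either to the investigator or to a blinded Medical Monitor, so that 6.7 can operate.
3. Name BMD in the list of data for DMC review in section 7.
4. State how a Day 292 BMD finding is handled, since it falls outside the 30-day window for non-serious AEs.
5. If the charter or imaging manual already provides a route, refer to it in the protocol.

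What is then done clinically for a subject is for the sponsor to define. An explicit statement that BMD is assessed only as an endpoint and is exempt from 6.7 would also remove the textual conflict, but it would leave individual-level capture and awareness as they are.

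The cost is protocol wording and one extra report from scans already taken and read. The downside is a small theoretical clue to treatment. It is limited because the scheduled post-baseline scans come at or after the end of dosing and hepatic fat results stay withheld.

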5.11 Sampling for Additional Research

Where individual subjects have provided separate consent for Additional research collection, prospective samples of blood will be collected at selected time points (see [Table 5.5.1-1](#)) and banked. Additionally, residual serum from adiponectin, insulin and 7 α -hydroxy-cholesten-3-one (C4) collections will also be retained by the BMS Biobank for additional research purposes. No additional sampling is required for residual collections. Additional research collections and retention should be presented to all subjects, except where prohibited by local laws or regulations. However, enrollment into the main study is not contingent upon consent to participate in future additional research sample banking. Further details of sample collection and processing will be provided to the site in the procedure manual.

6 ADVERSE EVENTS

An *Adverse Event (AE)* is defined as any new untoward medical occurrence or worsening of a preexisting medical condition in a clinical investigation subject administered study drug and that does not necessarily have a causal relationship with this treatment. An AE can therefore be any unfavorable and unintended sign (such as an abnormal laboratory finding), symptom, or disease temporally associated with the use of study drug, whether or not considered related to the study drug.

The causal relationship to study drug is determined by a physician and should be used to assess all adverse events (AE). The causal relationship can be one of the following:

Related: There is a reasonable causal relationship between study drug administration and the AE.

Not related: There is not a reasonable causal relationship between study drug administration and the AE.

The term "reasonable causal relationship" means there is evidence to suggest a causal relationship.

Adverse events can be spontaneously reported or elicited during open-ended questioning, examination, or evaluation of a subject. (In order to prevent reporting bias, subjects should not be questioned regarding the specific occurrence of one or more AEs.)

6.1 Serious Adverse Events

A *Serious Adverse Event (SAE)* is any untoward medical occurrence that at any dose:

- results in death
- is life-threatening (defined as an event in which the subject was at risk of death at the time of the event; it does not refer to an event which hypothetically might have caused death if it were more severe)
- requires inpatient hospitalization or causes prolongation of existing hospitalization (see **NOTE** below)
- results in persistent or significant disability/incapacity
- is a congenital anomaly/birth defect
- is an important medical event (defined as a medical event(s) that may not be immediately life-threatening or result in death or hospitalization but, based upon appropriate medical and scientific judgment, may jeopardize the subject or may require intervention [e.g., medical, surgical] to prevent one of the other serious outcomes listed in the definition above.) Examples of such events include, but are not limited to, intensive treatment in an emergency room or at home for allergic bronchospasm; blood dyscrasias or convulsions that do not result in hospitalization.) Potential drug induced liver injury (DILI) is also considered an important medical event. (See [Section 6.6](#) for the definition of potential DILI.)

Suspected transmission of an infectious agent (e.g., pathogenic or nonpathogenic) via the study drug is an SAE.

Although pregnancy, overdose, cancer, and potential drug induced liver injury (DILI) are not always serious by regulatory definition, these events must be handled as SAEs. (See [Section 6.1.1](#) for reporting pregnancies).

NOTE:

The following hospitalizations are not considered SAEs in BMS clinical studies:

- a visit to the emergency room or other hospital department < 24 hours, that does not result in admission (unless considered an important medical or life-threatening event)
- elective surgery, planned prior to signing consent
- admissions as per protocol for a planned medical/surgical procedure
- routine health assessment requiring admission for baseline/trending of health status (e.g., routine colonoscopy)
- medical/surgical admission other than to remedy ill health and planned prior to entry into the study. Appropriate documentation is required in these cases

- admission encountered for another life circumstance that carries no bearing on health status and requires no medical/surgical intervention (e.g., lack of housing, economic inadequacy, caregiver respite, family circumstances, administrative reason).
- Admission for administration of anticancer therapy in the absence of any other SAEs (applies to oncology protocols)

6.1.1 Serious Adverse Event Collection and Reporting

Sections 5.6.1 and 5.6.2 in the Investigator Brochure (IB)⁷ represent the Reference Safety Information to determine expectedness of serious adverse events for expedited reporting. Following the subject's written consent to participate in the study, all SAEs, whether related or not related to study drug, must be collected, including those thought to be associated with protocol-specified procedures. All SAEs must be collected that occur during the screening period and within 30 days of discontinuation of dosing. If applicable, SAEs must be collected that relate to any later protocol-specified procedure (e.g., a follow-up skin biopsy).

The investigator should report any SAE that occurs after these time periods and that is believed to be related to study drug or protocol-specified procedure.

An SAE report should be completed for any event where doubt exists regarding its seriousness.

If the investigator believes that an SAE is not related to study drug, but is potentially related to the conditions of the study (such as withdrawal of previous therapy or a complication of a study procedure), the relationship should be specified in the narrative section of the SAE Report Form.

SAEs, whether related or not related to study drug, and pregnancies must be reported to BMS (or designee) within 24 hours. SAEs must be recorded on the SAE Report Form; pregnancies on a Pregnancy Surveillance Form (electronic or paper forms). The preferred method for SAE data reporting collection is through the eCRF. The paper SAE/pregnancy surveillance forms are only intended as a back-up option when the eCRF system is not functioning. In this case, the paper forms are to be transmitted via email or confirmed facsimile (fax) transmission to:

SAE Email Address: Refer to Contact Information list.

SAE Facsimile Number: Refer to Contact Information list.

For studies capturing SAEs through electronic data capture (EDC), electronic submission is the required method for reporting. The paper forms should be used and submitted immediately, only in the event the electronic system is unavailable for transmission. When paper forms are used, the original paper forms are to remain on site.

SAE Telephone Contact (required for SAE and pregnancy reporting): Refer to Contact Information list.

If only limited information is initially available, follow-up reports are required. (Note: Follow-up SAE reports should include the same investigator term(s) initially reported.)

If an ongoing SAE changes in its intensity or relationship to study drug or if new information becomes available, a follow-up SAE report should be sent within 24 hours to the BMS (or designee) using the same procedure used for transmitting the initial SAE report.

All SAEs should be followed to resolution or stabilization.

6.2 Nonserious Adverse Events

A *nonserious adverse event* is an AE not classified as serious.

6.2.1 Nonserious Adverse Event Collection and Reporting

The collection of nonserious AE information should begin at initiation of study drug. Nonserious AE information should also be collected from the start of a placebo lead-in period or other observational period intended to establish a baseline status for the subjects.

Nonserious AEs should be followed to resolution or stabilization, or reported as SAEs if they become serious (see [Section 6.1.1](#)). Follow-up is also required for nonserious AEs that cause interruption or discontinuation of study drug and for those present at the end of study treatment as appropriate. All identified nonserious AEs must be recorded and described on the nonserious AE page of the CRF (paper or electronic).

Completion of supplemental CRFs may be requested for AEs and/or laboratory abnormalities that are reported/identified during the course of the study.

6.3 Laboratory Test Result Abnormalities

The following laboratory test result abnormalities should be captured on the nonserious AE CRF page or SAE Report Form (paper or electronic) as appropriate:

- Any laboratory test result that is clinically significant or meets the definition of an SAE
- Any laboratory test result abnormality that required the subject to have study drug discontinued or interrupted
- Any laboratory test result abnormality that required the subject to receive specific corrective therapy.

It is expected that wherever possible, the clinical rather than laboratory term would be used by the reporting investigator (e.g., anemia versus low hemoglobin value).

6.4 Pregnancy

If following initiation of the investigational product, it is subsequently discovered that a study subject is pregnant or may have been pregnant at the time of study exposure, including during at least 5 half lives after product administration, the investigator must immediately notify the BMS Medical Monitor/designee of this event and complete and forward a Pregnancy Surveillance Form to BMS Designee within 24 hours and in accordance with SAE reporting procedures described in [Section 6.1.1](#).

In most cases, the study drug will be permanently discontinued in an appropriate manner (e.g., dose tapering if necessary for subject safety).

In the rare event that the benefit of continuing study drug is thought to outweigh the risk, after consultation with BMS, the pregnant subject may continue study drug after a thorough discussion of benefits and risk with the subject.

Protocol-required procedures for study discontinuation and follow-up must be performed on the subject unless contraindicated by pregnancy (e.g., x-ray studies). Other appropriate pregnancy follow-up procedures should be considered if indicated.

The investigator must immediately notify the BMS (or designee) Medical Monitor of this event and complete and forward a Pregnancy Surveillance Form to BMS (or designee) within 24 hours and in accordance with SAE reporting procedures described in [Section 6.1.1](#).

Follow-up information regarding the course of the pregnancy, including perinatal and neonatal outcome and, where applicable, offspring information must be reported on the Pregnancy Surveillance Form.

Any pregnancy that occurs in a female partner of a male study participant should be reported to BMS. Information on this pregnancy will be collected on the Pregnancy Surveillance Form.

